--	---

	
review the available data at the time of the first dosing and the measured GFR and PV data for the first dosing day will be provided. The DAC will then be asked to fill out a survey asking whether the mGFR and PV data would have influenced their treatment decision, and if so, indicate what they would have done differently.
 
Following the evaluation of mGFR and PV data at the time of the initial VFI dose, the mGFR and PV data determined from the second VFI dosing point will be provided to the DAC. The DAC will then be asked to fill out a separate survey asking how the actual measured PV and GFR differ from the clinical assessments, whether the mGFR and PV data would influence their treatment decision, and if so, indicate what they would have done differently.
 
After all assessments have been completed, the DAC will review the results of their analyses and compile a summary report on the secondary endpoints as well as their assessment of the overall impact of the PV and mGFR on clinical decision making.

Total number of patients	We plan to enrol 50 eligible patients. Due to the explorative nature of this phase II study a formal sample size calculation is not possible. However, the sample size of 50 patients is sufficient to guarantee reasonable accuracy with respect to the main objectives of the trial as specified below.
Study population	Male and Female patients aged $\geq 18$ admitted to the hospital ward with a diagnosis of congestive heart failure.

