**Table 10: Adjudication Committee Evaluation**

Would FAST GFR and PV measurements have changed clinical management overall?

Would the FAST GFR and PV measurement on day 1 have led to applying a different diuretics dosage between day 1-3?

Would the FAST GFR and PV measurement on day 3 have led to applying a different dosage between day 3-5?

Would the FAST GFR and PV measurement on day 1 have led to choosing dialysis/ultrafiltration instead of diuretics escalation between day 1-3?

Would the FAST GFR and PV measurement on day 1 have led to choosing diuretics escalation instead of dialysis/ultrafiltration between day 1-3?

Would the FAST GFR and PV measurement on day 3 have led to choosing dialysis/ultrafiltration instead of diuretics escalation between day 3-5?

Would the FAST GFR and PV measurement on day 3 have led to choosing diuretics escalation instead of dialysis/ultrafiltration between day 3-5?

\*Responses will be collected as a Yes/No, with an additional free text section available to record details to substantiate the response

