- To evaluate (by an adjudication committee) whether clinical decision making would have been affected by adding FAST GFR and PV measurements to clinical routine including the following questions:
  - Would FAST GFR and PV measurements have changed clinical management overall?
  - Would the FAST GFR and PV measurement on day 1 have led to applying a different diuretics dosage between day 1-3?
  - Would the FAST GFR and PV measurement on day 3 have led to applying a different diuretics dosage between day 3-5?
  - Would the FAST GFR and PV measurement on day 1 have led to choosing dialysis/ultrafiltration instead of diuretics escalation between day 1-3?
  - Would the FAST GFR and PV measurement on day 1 have led to choosing diuretics escalation instead of dialysis/ultrafiltration between day 1-3?
  - Would the FAST GFR and PV measurement on day 3 have led to choosing dialysis/ultrafiltration instead of diuretics escalation between day 3-5?
  - Would the FAST GFR and PV measurement on day 3 have led to choosing diuretics escalation instead of dialysis/ultrafiltration between day 3-5?

To evaluate this endpoint an adjudication committee will be convened to analyse the outputs of the study after its completion. The goal of the adjudication committee is to the best of their ability describe any changes in treatment they would have made to each patient based had the mPV and mGFR metrics been available during the episode of care. No clinical decisions will be made based on the results generated by the FAST PV and mGFR Technology as results will not be made available to the treating physicians and will only be released to the adjudication committee after the last patient has been discharged. We will calculate absolute and relative frequencies of the “yes”-answers to the questions specified above together with 95% confidence intervals.

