or TBVS between Day 1 and 3 had significantly different percentage change of mGFR between Day 1 and Day 3 compared to patients with a high PVS or TBVS and an increasing PVS between Day 1 and 3, t-Tests or Mann-Whitney-U-tests will be used depending on the distribution of the values.

To evaluate whether Patients with a low PVS or TBVS on Day 1 (<-10%) and an increasing PVS or TBVS between Day 1 and 3 had significantly different percentage change of mGFR between Day 1 and Day 3 compared to patients with a low PVS or BCS and a decreasing PVS between Day 1 and 3, t-Tests or Mann-Whitney-U-tests will be used depending on the distribution of the values.

To evaluate whether patients with an improving (i.e. increasing) mGFR from day 1 to day 3 differ significantly from patients with a worsening (i.e. decreasing) mGFR regarding baseline characteristics (see chapter 4.1), mPVS, mTBVS, ePVS, eTBVS, and remaining length of stay appropriate tests depending on the distribution will be used (t-Test or Mann-Whitney-U-test for continuous variables and chi-square tests or Fisher-Boschloo-tests for categorical variables).

To evaluate whether disagreement between the physicians response to the question what they thought the intravascular volume of the patient was doing (increasing, decreasing, no change, treating physicians assessment Day 3) and the direction of measured change in TBVS is associated with a longer remaining length of stay, a t-test or Mann-Whitney-U-test depending on the distribution will be used. A measured change in TBVS of more than 5% between Day 1 and 3 was determined as a significant change.

To evaluate (by an adjudication committee) whether clinical decision making would have been affected by adding FAST GFR and PV measurements to clinical routine, the following questions were to be answered:

- How would you alter the intensity of Diuretic Therapy given on Day 1 and Day 3?
- How would you alter the intensity of RAASI Therapy given Day 1 and Day 3?  
How would you alter the intensity of Beta Blocker Therapy given Day 1 and Day 3?
- How would you alter the intensity of other GDMT given Day 1 and Day 3?

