To evaluate this endpoint an adjudication committee will be convened to analyse the outputs of the study after its completion. The goal of the adjudication committee is to the best of their ability describe any changes in treatment they would have made to each patient had the mPV and mGFR metrics been available during the episode of care. No clinical decisions will be made based on the results generated by the FAST PV and mGFR Technology as results will not be made available to the treating physicians and will only be released to the adjudication committee after the last patient has been discharged.

The scale to define the intensity of changes reaches from 1 to 5 meaning from much less intense to much more intense (3 is no change).

Absolute and relative frequencies of the changes to the questions specified above will be calculated for the whole assessment and separately for Day 1 and Day 3.

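### The adjudication committee records no decision without FAST, so its change rate cannot separate an effect of FAST from ordinary disagreement with the treating physician

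*Protocol*

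**What the plan says.** The protocol synopsis (Study design) sets the order. The committee reviews the data available at first dosing, and "the measured GFR and PV data for the first dosing day will be provided". The next step is the survey, which asks "whether the mGFR and PV data would have influenced their treatment decision". Day 3 runs the same way: "the mGFR and PV data determined from the second VFI dosing point will be provided to the DAC", followed by a separate survey.

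Protocol Table 10 has seven yes/no questions with free text, worded as attribution to FAST, for example "Would the FAST GFR and PV measurement on day 1 have led to applying a different diuretics dosage between day 1-3". Protocol section 14 reports the share of yes answers with 95% confidence intervals.

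SAP 7.7.1 uses different questions. The first is "How would you alter the intensity of Diuretic Therapy given on Day 1 and Day 3"; the others cover RAAS inhibitors, beta blockers and other guideline-directed therapy. Answers go on a five-point scale centred on no change, and the frequencies of changes are tabulated overall and by day. The stated task is to "describe any changes in treatment they would have made to each patient had the mPV and mGFR metrics been available". The same section says that treating physicians do not receive FAST results.

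**The concern.** To say that a measurement would have changed a decision, one needs the decision without it and the decision with it, from the same decision maker. Only the second is collected. Under the SAP items the comparator is the therapy given, chosen by other clinicians. A committee that simply favours more or less diuretic than the ward would score a change whatever FAST showed.

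The protocol's hypotheses include that decision making would have been improved in some patients had FAST been available. This is the only endpoint that asks directly whether decisions would differ. A descriptive rate must still describe what it is named for, and a confidence interval around it covers sampling error only.

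**Working it through.** **Is a decision without FAST recorded anywhere?** The places that describe the committee are the protocol synopsis, protocol section 4.4 with Table 10, protocol section 14, the SAP paragraph on blinding, and SAP 7.7.1. None provides for a committee rating made and recorded before FAST is shown. Table 10 collects yes/no plus free text, with no field for such a decision.

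**What is the reference for a change?**
- Protocol: the committee's own decision without FAST, imagined after FAST has been seen.
- SAP: the therapy given by clinicians without FAST. The item does not name FAST.

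**How large could the mixing be?** The plan has no figure to reproduce. It sets 50 patients on feasibility grounds and states no expected change rate. The following is an illustration under the SAP scoring, for one item on one day, with all 50 patients rated.

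Inputs:
- n = 50 (protocol section 14, size estimation).
- d = share of patients in whom the committee would differ from the ward without FAST. Not in the documents; assumed 10 to 40%.
- f = share in whom FAST changes the committee's own decision, taken as independent of d. Not in the documents; 0 and 20% are used.

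Two bounding cases for the reported rate r:
- A, a dissenting committee still differs from the ward after FAST: r = 1 − (1 − d)(1 − f).
- B, every FAST-induced switch in a dissenting case restores agreement with the therapy given and scores 3: r = d(1 − f) + (1 − d)f.

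| d | f = 0 | f = 20%, case A | f = 20%, case B |
|---|---|---|---|
| 10% | 10% | 1 − 0.90 × 0.80 = 28% | 0.08 + 0.18 = 26% |
| 20% | 20% | 1 − 0.80 × 0.80 = 36% | 0.16 + 0.16 = 32% |
| 40% | 40% | 1 − 0.60 × 0.80 = 52% | 0.32 + 0.12 = 44% |

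If f = 0, the expected results with exact 95% intervals are 5/50 (3.3 to 21.8%) at d = 10%, 10/50 (10.0 to 33.7%) at d = 20% and 20/50 (26.4 to 54.8%) at d = 40%. A pure FAST effect (d = 0, f = 20%) also gives 10/50 with the same interval as d = 20%, f = 0. The data cannot tell these two apart.

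**Direction.** In case A, r − f = d(1 − f), which is never negative. In case B, r − f = d(1 − 2f), which is negative once f exceeds 50%.

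**With a locked rating first.** If FAST has no effect and the committee is consistent between rounds, the expected count of switches is 0/50 (exact 95% interval 0 to 7.1%), whatever d is.

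**The case against.** The strongest reply is that both documents frame the task as attribution. The protocol survey concerns the committee's own decision, and the Table 10 questions ask what FAST would have led to or changed. A careful member who would have differed from the ward anyway should answer no. The SAP items are also introduced as bearing on the effect of adding FAST. Three of the four SAP items omit the word *on* after *given*, so they could be read as asking for changes in light of the Day 1 and Day 3 results.

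This limits the point. A reader might infer that the plan counts every disagreement with the ward as an effect of FAST. The protocol wording does not support that: disagreement can enter, but raters are asked to leave it out. Nor do the documents say that clinical and FAST data arrive at the same moment; the committee may look at the clinical data first. What stands is that no decision without FAST is recorded, so the attribution cannot be checked. The other reading of *given* does not help, because the alteration is then measured from a starting point that nobody wrote down.

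The stakes are also limited. This is the last of eleven secondary objectives, and all analyses are declared descriptive. The primary safety and FD003 stability results do not depend on it.

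**Conclusion.** The point holds as a problem of attribution. The change rate in SAP 7.7.1 cannot separate an effect of FAST from the committee's ordinary disagreement with the treating physician, and the protocol version rests on an unverifiable counterfactual.

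A reader might go further and call the rate biased upward for certain. The documents do not support that: a committee that FAST moves back to the therapy given would score 3, so a real effect would be hidden. Upward bias is likely at modest effects but not guaranteed.

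The size is illustrative. It rests on an assumed d of 10 to 40%, on independence of d and f, and on the SAP scoring. If FAST has no effect, the reported rate equals d. At d = 20% and a true effect of 20%, it is 32 to 36%. This should be corrected, but it does not threaten the primary objective.

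**What to change.** For each patient-day, have the same committee rate the listed therapies from the clinical data alone and lock that rating. Then show FAST PV and mGFR and have it rate again on the same form. Define the endpoint as the within-committee change between the two ratings, with a 95% confidence interval. Report disagreement with the therapy given separately. By Day 3 the committee has already seen that patient's Day 1 FAST results, so the SAP should say whether the Day 3 change is meant as the addition made by the Day 3 results alone.

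The cost is one extra rating per patient-day, at most about 50 × 2 = 100, in committee time. No extra staff or patient procedures are needed, and treating physicians stay without FAST results. Inconsistency between rounds may count as change. State this as a limitation, or gauge it by re-rating a few cases without FAST.

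SAP section 3 describes enrolment in the past tense, so ratings may already exist. If they do, label the result as difference from the therapy given, not as an effect of FAST.

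Also reconcile the SAP 7.7.1 questions with those in protocol Table 10, protocol section 14 and SAP 1.1, which still lists the protocol's set. Declare the change in SAP section 8, which does not mention it.

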**Table 1: Schedule of Study Events/Examinations**

Study Timepoint	Data collected from chart prior to enrolling	Patient Enrolled and Dosed	Data collected between 1 st and 2 nd Dose	Patient 2 nd VFI Dose	Data Collected after 2 nd Dose	Data Collected Before Discharge	Follow up in person or by phone call	Follow up phone call/ Follow up Visit for Pregnancy test if WOCBP
Visit	Pre-Dose	Day 1	Day 2	Day 3	Day 4	Day 5	Day 10	Day 30
Informed Consent	X							
Inclusion/ Exclusion Criteria Assessment	X							

Structural Heart Disease Criteria Assessment a		X						
Demographics b		X						
Comorbidities c		X						
Full medication list on enrollment into the study and during follow-up d		X	X	X	X	X		
Patient Symptom Assessment Survey e		X	X	X	X	X		
Clinical Presentation/ Exam f		X	X	X	X	X		
Treating Physician Survey g		X		X				
Study-Related Laboratory Measurements h		X	X	X	X	X		
Routine Clinical Parameters i	X*	X	X	X	X	X		
Clinical Data j	X*	X	X	X	X	X		
Adverse events		X	X	X	X	X	X	X
Blood specimen for marker analysis k		X		X				
Discharge from study								X
Adjudication Committee Evaluation l								X
WOCBP Pregnancy test m	X			X				X

a See Table 2 for Structural Heart Disease Criteria

b See Table 3 for specific demographic parameters

c See Table 4 for specific instructions on collecting comorbidities

d See Table 5 for specific instructions of collecting medications

e See Annex D for the Patients Symptom Assessment Survey

f See Table 6 for Clinical presentation/exam parameters

g See Annex E for the Treating Physician Survey

h See Table 7 for Study Related Laboratory Measurements

i See Table 8 for Routine Clinical Parameters

j See Table 9 for Clinical Data collected

k Blood Specimens for the determination of the FAST PV and mGFR will be taken pre-dose and at 15 ( $\pm$  5), 30 ( $\pm$  5), 60 (+30), and 180 (+120) minutes post-dose. Note that the 30 minute blood draw must be at least 10 minutes after the 15 minute blood draw, and the 180 minute blood draw must be at least 100 minutes after the 60 minute blood draw.

l See Table 10 for the Adjudication Committee Evaluation Questions; Adjudication Committee meets after all collected data available.

m See Table 11 for Details of Pregnancy test

\*will be collected retrospectively after study inclusion

Study objectives / endpoints	
Primary endpoint: Global aim is to assess the safety and function of the FAST PV and mGFR Technology in hospitalized patients with heart failure.
 
 
• Safety will be assessed by determination of the absolute and relative frequencies of AEs and SAEs related to VFI.
 
• Function of the FAST PV measurement will be assessed by determining the plasma stability of the FD003 high molecular weight marker over the 15, 30, and 60 minute blood draws and applying the following criteria: 
 
- The FAST PV measurement is considered as stable, if the mean plasma concentration of FD003 at 30 minutes is not more than 10% lower than the mean plasma concentration at 15 minutes AND if the mean plasma concentration at 60 minutes is not more than 10% lower than the mean plasma concentration at 30 minutes
 
- We will determine the percentage of patients which show a decline in the plasma concentration of FD003 of more than 10% from 15min to 30min and separately from 30 min to 60min. This percentage should be ideally close to 0.
 
 
 
 
Secondary Endpoints:
 
 
• To evaluate how estimated PV (ePV) and estimated total blood volume (TBV) assessments on days 1 and 3 (by established measures such as Nadler's formula or Metropolitan Life Tables) predict measured PV (mPV; as assessed by FAST methodology) and measured TBV (mTBV; calculated from mPV and measured hematocrit) at these time points.
 
• To evaluate how a clinical evaluation (including a reasonable subset of the variables age, gender, BMI, hematocrit, edema grade, presence of pulmonary rales, presence of jugular venous congestion, arterial blood pressure, NYHA stage, respiratory rate) on days 1 and 3 predicts mPV and mTBV at these time points.
 
• To evaluate whether eGFR calculation by the CKD-EPI formula on days 1 and 3 provides an accurate estimate of
 

-------------------------------------	---

	
measured GFR (mGFR; by assessed by FAST methodology) in heart failure patients undergoing active fluid management.
 
 
• To evaluate whether patients with a low mGFR/eGFR ratio on days 1 and 3 are at higher risk of developing AKI within the following 48-72 hours.
 
• To evaluate whether ranges of mPV (low mPV, normal mPV, high mPV) and/or mTBV (low mTBV, normal mTBV, high mTBV) on days 1 and 3 are associated with subjectively reported symptoms (PGA, dyspnea, dizziness, nausea) determined using patient symptom assessment sheets within the following 24-48 hours.
 
• To evaluate whether patients with low mPV or low mTBV (cutoffs potentially adjusted for some of the following variables age, gender, body height, body weight, optimal body weight (dry weight), hematocrit) on day 1 or on day 3 are at risk of developing low-output complications within the next 24-48 hours (e. g. subjectively reported dizziness/nausea, PGA, hypotension, need for iv-fluid therapy).
 
• To evaluate whether patients with a high mPV or a high mTBV (cutoffs potentially adjusted for some of the following variables age, gender, body height, body weight, optimal body weight (dry weight), hematocrit) on day 1 and/or day 3 are at risk of being refractory to diuretic therapy (e. g. require dosage increases of furosemide/torsemide, require ultrafiltration/RRT within the next 24-48 hours, fail to improve subjectively in PGA and dyspnea scales).
 
• To evaluate whether the time course of ePV and estimated TBV (eTBV) from day 1 to day 3 adequately reflects the time course of mPV and mTBV at these time points.
 
• To evaluate whether the change of mPV and mTBV from day 1 to day 3 is predictive of length of stay, dialysis/ultrafiltration requirement, or rehospitalization within 30 days, or mortality.
 
• To evaluate whether the time course of mGFR from day 1 to day 3 correlates temporally with or predicts the time course of eGFR within the next 24-48 hours.
 
• To evaluate (by an adjudication committee) whether clinical decision making would have been affected by adding FAST GFR and PV measurements to clinical
 

--	---

[figure not shown]
	
routine including the following questions:
 
 
○ Would FAST GFR and PV measurements have changed clinical management overall?
 
○ Would the FAST GFR and PV measurement on day 1 have led to applying a different diuretics dosage between day 1-3?
 
○ Would the FAST GFR and PV measurement on day 3 have led to applying a different diuretics dosage between day 3-5?
 
○ Would the FAST GFR and PV measurement on day 1 have led to choosing dialysis/ultrafiltration instead of diuretics escalation between day 1-3?
 
○ Would the FAST GFR and PV measurement on day 1 have led to choosing diuretics escalation instead of dialysis/ultrafiltration between day 1-3?
 
○ Would the FAST GFR and PV measurement on day 3 have led to choosing dialysis/ultrafiltration instead of diuretics escalation between day 3-5?
 
○ Would the FAST GFR and PV measurement on day 3 have led to choosing diuretics escalation instead of dialysis/ultrafiltration between day 3-5?
 

Safety	Adverse events (AEs) will be collected and evaluated as they occur throughout the study.
Discontinuation criteria	
Individual Patient Discontinuation Criteria:  A patient is free to withdraw consent and discontinue participation in the study at any time, without prejudice to further treatment according to standard clinical practice. The investigator may remove a patient if, in the investigator's judgment, continued participation would pose unacceptable risk to the patient or to the integrity of the study data. All procedures for early termination must be completed. Reasons for removal or withdrawal may include:
 
 
• Admission to the ICU prior to either the first or second dose
 
• The patient develops a stated exclusion criterion during the course of study
 
• If the patient experiences an acute anaphylactoid reaction during the course of administering the FAST VFI, administration will stop immediately
 
• Evidence of an anaphylactoid reaction (dyspnea, urticaria, flush, bronchospasm, or severe systemic hypotension)
 
• Administrative decision by the investigator or sponsor
 
• Significant protocol deviation
 
• Patient noncompliance
 
• Safety concern by the investigator or sponsor
 
• Lost to follow-up
 
• Pregnancy
 

	
Patients who are withdrawn for reasons other than safety issues may be replaced at the discretion of the sponsor and investigator.
 
In the event of a patient's withdrawal, the investigator makes every effort to complete the EOS assessments. All withdrawn patients with ongoing clinically significant clinical or laboratory findings will be followed until the finding is resolved or medically stable; reasonable attempts will be made to follow-up with patients.
 
Study Discontinuation Criteria:
 
 
• Unjustifiable risk and toxicity in risk-benefit analysis (decision taken by principal Investigator)
 
• New scientific evidence provided during the study that could affect the patient's safety (benefit-risk analysis no longer positive)
 
• Decision of the Sponsor or the Competent Authority that the study should be discontinued.
 

Statistical analysis	Descriptive statistics will be performed for safety assessments and for relationship between the FAST GFR and other measurements of renal function as well as between the FAST PV and other assessments of plasma volume.
Pharmacological-toxicological evaluation	Pharmacokinetics of the FAST VFI will not be evaluated as a part of this study, but these parameters have been investigated in previous clinical and nonclinical studies.
Risk-benefit analysis	
Risks of treatment methods: Usual risks of participating in clinical trials, which are related to possible allergic reactions and blood drawing via venipuncture.
 
Risks (IMP) (according to the reference safety information) Possible allergic reactions and risks associated with dosing and blood drawing via venipuncture.
 
Action steps for risks minimisation: The FAST Technology has been previously used in three clinical studies. 87 patients have been dosed with the FAST VFI. There have been no reported SAEs and few minor AEs across all studies. Existing allergen risks in patients will be included as part of informed consent and staff will be well trained prior to the study initiation.
 
Remaining risk: Possible allergic reactions and risks associated with dosing and blood drawing via venipuncture.

	
Benefit: A rapid and accurate measurement of plasma volume (PV) and glomerular filtration rate (GFR) is important in chronic heart failure (CHF), acute kidney injury (AKI) and chronic kidney disease (CKD) for assessment of impairment, diagnosis, and prompt treatment. This study primarily serves the purpose of obtaining information about the tolerability and safety of the FAST PV and mGFR Technology in CHF patients.
 
There are no perceived direct benefits to patients participating in this trial. However, thorough medical check-ups may be seen as an advantage. The safety of the patients will be observed during all study phases.
 
Medical progress is based on research which ultimately must rest in part on experimentation involving humans. Eligible patients may consider participation in this clinical trial because they want to contribute to the advancement of medical knowledge. Still, considerations related to the well-being of the individual patients enrolled into this clinical study must take precedence over the interests of science and society. Based on available information and the design of the study, the sponsor and the investigator consider the trial to be ethically acceptable. The duration of hospitalization and the medical surveillance are considered adequate to ensure safety of the patients.


Contraindications:
 
Procedures in case of emergency:
 
Treatment of overdose:
	
The FAST VFI (FD004) should not be administered to patients with known hypersensitivity to dextran, 5 aminofluorescein dye, or 2-sulfohexamine rhodamine dye.
 
The FAST VFI (FD004) was well tolerated in the nonclinical studies conducted to date. Anaphylactic responses to dextrans, while rare, must be considered as a possibility for the high molecular weight dextrans being evaluated by FAST. As such, all testing facilities should have immediately available procedures to administer treatment for an anaphylactic response should it occur.
 
The FAST VFI is contained in single-dose vials, making significant overdose unlikely. Though the vials are overfilled with 4mL/62.6 mg in order to ensure that a full 3mL/47mg dose can be drawn, previous studies have evaluated the safety of the VFI using a 3mL/150mg dose, over two times the amount of material contained in the single-dose vials for this study. There is no known antidote for overdose of VFI. In the event of a suspected overdose, the patient should be monitored appropriately and should receive supportive therapy, as necessary.

Timetable	
Date of study / recruitment start (first patient first visit (FPFV): January 2019
 
End of recruitment: Anticipated to be July 2019
 
End of trial (last patient last visit, LPLV): Anticipated to be August 2019
 
Trial duration (for a patient): 33 Days
 
Follow up: Patients will receive a follow-up phone call on Day 7 and Day 30 after the second VFI dose

Funding	The study will be supported by a research grant from FAST BioMedical.
Key words	Congestive Heart Failure, Acute Kidney Injury, Plasma Volume, Clinical Management, Glomerular Filtration Rate (GFR), Plasma Volume (PV), FAST VFI, FAST PV and mGFR Technology,

